The low plasma levels have not been associated with hemodynamic instability nor have they been associated with changes in cardiac contractility. No interactions with the autonomic nervous system have been reported and there are no known effects on sinoatrial conduction. Lidocaine is metabolized by the liver, with less than 10% excreted in urine. Complications are rare. Despite concerns for arrhythmias, intravenous lidocaine has been used in cardiothoracic surgery without increased rates of cardiac complications. Given this volume of evidence, we feel that intravenous lidocaine in the setting of AIS surgery is safe.

3.b Treatment Regimen

After a 1mg/kg IBW lidocaine bolus with induction, a lidocaine 1 mg/kg/hr (IBW) IV infusion with maximum dose of 200 mg/hr or D5W (placebo) at equal volume rate of administration will begin prior to skin incision and continue intraoperatively for duration of the case. Study drug will be discontinued upon 24 hours of stay in either PACU or PICU postoperatively.

Method for Assigning Subjects to Treatment Groups

Patients consenting to randomization will be randomized 1:1 to the control vs study groups. A permuted randomized block approach¹ with blocks of size 4, 6 and 8. Given the relatively large number of patients to be enrolled, no stratification will be performed. After 30 patients are enrolled, an interim analysis, without unblinding, of baseline covariates will be performed to ensure equal distribution between groups. If distribution is uneven for covariates concerning for confounding, then stratification by these covariates will be employed to ensure equal distribution with randomization.

3.c Blinding of Study Drug

This is a Phase IV, randomized, triple-blind, placebo-controlled trial with two study groups: postoperative standard of care with opioid patient controlled analgesia (PCA) and IV lidocaine infusion versus postoperative standard of care plus normal saline placebo. Block randomization into one of the two groups will be based on a random table generated using an R-program. Group 1 (Study) will receive intravenous lidocaine during and after posterior spinal fusion for AIS. Group 2 (Control) will receive saline placebo during and after surgery.

F Study Procedures

F1 Screening for Eligibility

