The anticipated outcome is decreased in-hospital opioid consumption for those patients treated with intravenous lidocaine. Other anticipated outcomes are improved recovery as measured by PROMIS-M and PROMIS-PI measures at 6 weeks, 3 months, 6 months, and 12 months after surgery. We anticipate that the anti-inflammatory effect of lidocaine will reflect a smaller postoperative inflammatory response as measured by IL-10, IL-4, and IL-12.

F3 Safety and Adverse Events

Serum lidocaine levels will be drawn at 12 hours after incision and reviewed by an individual independent from the study team. Lidocaine toxicity will result in immediate cessation of study drug, unblinding, and reporting to the Medical Monitor and IRB. If intraoperative surgical, medical, or anesthetic complications occur, including cardiac arrhythmia, the study medication will be stopped and the patient withdrawn from the study. The patient will be analyzed in an intent-to-treat analysis, though they will be excluded from as-treated analyses. After surgery, patients will be seen and examined twice daily with attention to postoperative complications. As the study-drug will have completed infusion, all complications will be recorded though patients will remain enrolled in the study and analyzed per-protocol. All adverse events will be recorded up to 12 weeks after surgery. These will be captured via interview at the visit or via telephone if a clinic visit is not possible. Readmission for any reason will be recorded and details of this hospitalization will be recorded. Any reason reasonably related to the research protocol will be reported to the Medical Monitor and the IRB.

We believe there are minimal risks associated with participation in this clinical trial and with the study intervention (intravenous lidocaine). The most concerning serious adverse event that might be attributed to systemic lidocaine administration is cardiac arrhythmia/arrest. Therapeutic serum concentrations are far lower than toxic levels and we believe the risk of serious adverse events to be low. The intervention will not add time to the surgical intervention and, thus, does not pose additional risk from this perspective. All patients will receive standard of care treatment before, during, and after surgery and the study intervention will pose no risk to this.

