Safety measures to minimize/eliminate risks to human subjects and study personnel include the use of the Medical Monitor and immediate reporting of any adverse (expected or unexpected) to the project PI and project manager. If any intraoperative complications occur, such as but not limited to cardiac arrest or seizure, the study medication will not be administered and the patient will be excluded from the study. However, if one of these problems occurs after the application of the study medication the patient will be unblinded. The patient will be followed for the occurrence of further adverse events or complications.

For any serious adverse event, the Medical Monitor at the enrollment site will perform a root cause analysis and will notify the project PI in the study medication is believed to be a potential cause of the adverse event. The Monitor may recommend stopping the study. Any serious adverse event will be reported to the PI and the IRB within 10 working days.

F4 Study Outcome Measurements and Ascertainment

The primary outcome measure is total, in-hospital opioid consumption following surgery for thoracolumbar trauma. Opioid consumption will be measured in morphine-equivalent dosage (MED), to allow for the use of different opioid medications (e.g. fentanyl, hydromorphone, oxycodone) over the course of care.

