After the first 15 patients are enrolled, a group consisting of the Principal Investigator and an unengaged physician will review the AE/SAE data. The data will be reviewed blinded. If intraoperative surgical, medical, or anesthetic complications occur, including cardiac arrhythmia, the study medication will be stopped and the patient withdrawn from the study. The patient will be analyzed in an intent-to-treat analysis, though they will be excluded from as-treated analyses. After surgery, patients will be seen and examined twice daily with attention to postoperative complications. As the study-drug will have completed infusion, all complications will be recorded though patients will remain enrolled in the study and analyzed per-protocol.

Special attention will be given if adverse events occur in a higher frequency than expected given patient age and health condition. Serious adverse events, or those that are life threatening, result in death, prolonged hospitalization, readmission, cause persistent disability or require urgent intervention to prevent permanent morbidity will be monitored for up to 30 days after the drug is administered. If there appears to be an imbalance in AE/SAE, unblinding and analysis will ensue to determine if the study should continue. Early termination will occur if SAEs are linked to the treatment arm.

After 10 patients have completed the hospital phase of the study, flow and mass cytometry will be performed to ensure we are capturing cell types and signaling proteins as anticipated.

All protocol violations and SAE's will be reported to HRPO within the WU HRPO policies and procedures reporting guidelines
SAEs will be tracked through resolution.

J References

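### Section F3 unblinds every dosed patient who has any intraoperative complication, whether or not care depends on knowing the arm; a minor conduct rule that is cheap to tighten

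*Combined protocol and SAP*

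**What the plan says.** Section F3 (Safety and Adverse Events) deals with intraoperative complications in two places.

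- **Risk-minimisation paragraph of F3.** The trigger is "If any intraoperative complications occur, such as but not limited to cardiac arrest or seizure". If the event comes before dosing, "the study medication will not be administered and the patient will be excluded from the study". For a patient already dosed, "if one of these problems occurs after the application of the study medication the patient will be unblinded", with follow-up for further events.
- **Opening paragraph of F3, repeated in section I1.** "If intraoperative surgical, medical, or anesthetic complications occur, including cardiac arrhythmia, the study medication will be stopped" and the patient is withdrawn. Then: "The patient will be analyzed in an intent-to-treat analysis, though they will be excluded from as-treated analyses". Unblinding is not mentioned for these events.

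There are two other unblinding triggers, and both concern different events. F3 has one for toxicity: "Lidocaine toxicity will result in immediate cessation of study drug, unblinding, and reporting to the Medical Monitor and IRB". I1 has one for an apparent imbalance in adverse events across the trial.

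On timing of dosing, section E3 (3.b Treatment Regimen) begins "After a 1mg/kg IBW lidocaine bolus with induction", and the infusion starts before incision. Section 3.c calls the trial triple-blind and places opioid PCA in postoperative care. Section F2 defines the primary outcome as total in-hospital opioid consumption after surgery, in morphine equivalents.

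**The concern.** Breaking the blind for a cardiac arrest, a seizure or suspected lidocaine toxicity is proper. The F3 rule goes further. It requires unblinding after any intraoperative complication in a dosed patient, including one whose management would be the same in either arm. Nothing says who decides, when the code is broken or who is told, and no emergency code-break procedure appears elsewhere.

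The primary outcome accrues after the operation, so disclosure at the time of the event would come before it. PCA makes part of that outcome depend on the patient's own behaviour. If the patient or the staff managing analgesia learn the arm, opioid use in that patient is no longer a blinded outcome, yet the patient stays in the intent-to-treat analysis.

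A second, smaller matter is that F3 and I1 promise an intent-to-treat analysis while taking these patients out of the study. Unless outcome collection continues, that analysis lacks data for them. The pre-dosing exclusion in F3 is a narrow case of the same problem when the patient has already been randomised.

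**Working it through.** **1. Reading the rules side by side.**

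| Event | F3, risk-minimisation paragraph | F3 opening paragraph and I1 |
|---|---|---|
| Intraoperative complication before dosing | Withhold drug, exclude | No separate rule |
| Intraoperative complication after dosing | Unblind, follow up | Stop drug, withdraw, keep in ITT, leave out of as-treated |
| Lidocaine toxicity | Not named | Stop drug, unblind, report (F3) |
| Apparent adverse event imbalance | Not covered | Unblind and analyse (I1) |

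The post-dosing problems in F3 refer back to the open list, so the sentence itself does not restrict them to arrest and seizure. For a dosed patient every action in the second row can be carried out together. The two columns differ in what they mention, and neither forbids what the other requires.

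**2. Timing.** The bolus comes with induction and surgery follows, so almost all intraoperative complications fall on the unblinding branch and very few on the exclusion branch.

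**3. The plan's own figures (section G1).** Mean 149 mg, SD 37 mg, d = 0.8, 25 per group, two-sided 0.05.
- Target difference: 0.8 × 37 = 29.6 mg; 29.6/149 = 19.9%, matching the stated 20% or so.
- Power at 25 per group: 80.7% (normal approximation), 79.1% (t-test). The stated 80% reproduces.

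**4. Illustrative size of bias.** The documents give neither a complication rate nor an effect of knowing the arm, so both are assumed. Let k patients, across both arms, be unblinded to themselves or to those managing their analgesia, and let each shift opioid use by δ in the direction expected of the arm. The arm difference then moves by k × δ/25. The standard error of the difference is 37 × √(2/25) = 10.47 mg. The last column is the two-sided t-test false-positive rate with the variance held constant.

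| δ | k | Shift (mg) | % of 29.6 mg | False-positive rate |
|---|---|---|---|---|
| 14.9 mg (10% of mean) | 1 | 0.60 | 2.0% | 5.04% |
| | 3 | 1.79 | 6.0% | 5.32% |
| | 5 | 2.98 | 10.1% | 5.9% |
| 37 mg (1 SD) | 1 | 1.48 | 5.0% | 5.22% |
| | 3 | 4.44 | 15.0% | 7.0% |
| | 5 | 7.40 | 25.0% | 10.66% |

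A simulation with all five patients in the lidocaine arm, and the variance allowed to rise, gives about 9% in place of 10.66% for the last row. On assumed complication rates of 2%, 5% and 10%, the rule would reach about 1, 2.5 and 5 of 50 patients.

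**5. Pre-dosing exclusion.** Losing one patient (24 against 25) lowers t-test power from 79.1% to 78.3%.

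**The case against.** Most of the case on the other side stands.

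- **The rules do not contradict each other.** A reader might infer that F3 and I1 give opposing orders. They do not: one place adds unblinding where the other is silent. What remains is that staff consulting one paragraph would act differently from staff consulting the other.
- **Material bias is not shown.** A reader might take the false-positive rate of 9% to 11% as the likely consequence. It needs one patient in ten to be unblinded to the people who influence opioid use, and each to move a full SD in the favourable direction. F3 and I1 also stop study drug after these events, and sections D1 and E3 (3.a) give a half-life of 1.5 to 2 hours. Both arms are then off drug for most of the stay, so there is little reason to expect a full SD shift. Some expectation effect could remain.
- **Recipient and timing are unknown.** If only the Medical Monitor is told, or disclosure comes after discharge, the harm does not arise. The text does not say so, but it does not rule it out.
- **Section E1 does not help the concern.** Its reference to physician discretion is about anaesthesia, so it is not evidence that postoperative opioid dosing is discretionary. Only the PCA statement in 3.c shows that the outcome depends on behaviour.
- **Grave events may be what was meant.** The examples are arrest and seizure, and the paragraph that follows concerns serious events. But the list is expressly open, so the restriction has to be written in.
- **The pre-dosing exclusion is rare**, and an event before any blinded drug cannot be caused by treatment.

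None of this supplies a reason to unblind a patient whose care does not depend on the arm.

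**Conclusion.** The point holds as a minor improvement to trial conduct. As written, F3 requires needless unblinding of dosed patients, at a time that could precede the primary outcome, and the parallel text in F3 and I1 leaves unblinding out. That much rests on the wording and on the timing of the bolus, and no assumed figure is needed.

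The size of any bias cannot be derived from the documents. It is probably small: at a 10% shift in opioid use the false-positive rate stays between 5.04% and 5.9% for 1 to 5 affected patients, and larger figures need assumptions that are hard to defend once the drug is stopped. Any harm also depends on early disclosure to the patient or to the staff managing analgesia.

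A reader might go further and treat this as an error in the choice of analysis. The documents do not support that: intent-to-treat is already stated for these patients. What is missing is wording that keeps them blinded where possible and keeps their outcomes coming in.

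**What to change.** Amend F3 and I1 so that one rule applies throughout.

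1. **Unblinding.** Break the blind only when knowing the allocation is needed for clinical care, which includes suspected lidocaine toxicity, cardiac arrest and seizure. Disclose only to those who need it, keep the patient and the staff managing analgesia blinded where that is safe, and log the time, reason and recipients.
2. **Staying in the study.** Where F3 says "the study medication will not be administered and the patient will be excluded from the study", and where F3 and I1 say "the study medication will be stopped and the patient withdrawn from the study", provide only for withholding or stopping study drug. Keep collecting the primary outcome from the medical record for every randomised patient, so that the intent-to-treat analysis already stated can be carried out.

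The decision to stop study drug stays with the clinicians. The cost is minor rewording and an unblinding log. Section H1 already has staff extracting data from the medical record, so no added visits, tests or patients are needed.

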There are no prior studies investigating the use of intravenous lidocaine for the management of pain associated with adolescent idiopathic scoliosis surgery. As such, the dosage chosen comes from prior work in abdominal surgery and elective spine surgery^{18,19,22}. These studies have shown lidocaine to be effective in improving pain scores, reducing opioid consumption, and improving patient reported outcomes measures. Lidocaine will be given at the induction of anesthesia until 24 hours after arrival to the Post-Anesthesia Care Unit (PACU) or Pediatric Intensive Care Unit (PICU).

A research pharmacist not involved in the care of the patient will deliver lidocaine, 8mg/mL, in D5W (Baxter International, Deerfield, IL, USA), or D5W (Baxter International) to the operating room for continuous infusion. A separate bag containing 1mg/kg of lidocaine in D5W, or an identical volume of plain D5W, will be delivered for bolus delivery. All solutions will be packaged identically, to avoid accidental unblinding. The study pharmacy will report both loading bolus volume and volume/hr rate for the infusion in the electronic medical record. The total volume of study drug/placebo administered will be recorded.

E Study Design

E1 Overview or Design Summary

Anesthesia, other than the lidocaine, will be given as standard of care per physician discretion

Study Drug: After a 1 mg/kg lidocaine bolus with induction, a lidocaine 1 mg/kg (IBW)/hr IV infusion with maximum dose of 200 mg/hr or D5W (placebo) at equal volume rate of administration will begin prior to skin incision and continue intraoperatively for duration of the case. Study drug will be discontinued upon 24 hours of stay in PICU or PACU postoperatively. Study drug will be dosed according to ideal body weight (IBW). Patient height, weight, age, and gender will be delivered to the study pharmacy prior to the day of surgery for calculation of IBW and dosing parameters.

E2 Subject Selection and Withdrawal

Study participants will be AIS patients recruited from Orthopaedic Spine clinics at Center of Advance Medicine Barnes Jewish and St. Louis Children's hospitals. Given the single disease investigated, AIS, we anticipate that our results will be generalizable to AIS patients at other institutions. We will enroll 50 patients, 25 per group, over two years. Approximately 60 AIS surgeries are performed per year at our institution.

2.a Inclusion Criteria

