Secondary outcome measures to assess recovery are the Patient Reported Outcomes Measurement Information System (PROMIS) Mobility (M) and Pain Interference (PI) domains. PROMIS is a general measure of health administered over particular health domains. This instrument has been tested extensively and is reliable and precise.⁴⁵ Scores range from 0-100 and are normalized so that a score of 50 is the population mean, with 10 points representing a standard deviation is 10 points. For the Mobility domain larger scores represent more function; for the PI domain larger scores represent more pain. The instrument administered via computer-adaptive testing (CAT) to minimize question burden. The Scoliosis Research Society 22 (SRS-22) will be used in assessing the quality of life in AIS patients. The SRS-22r includes 22 items distributed among five different factors (pain, self-image/appearance, function/activity, mental health, and satisfaction with management). Each component includes five items, except for the “satisfaction with management”, which only contains two items. Secondary measures to assess the anti-inflammatory effect of lidocaine will be serum levels of IL-10, IL-4 and IL-12.

The anticipated outcome is decreased in-hospital opioid consumption for those patients treated with intravenous lidocaine. Other anticipated outcomes are decreased opioid consumption at three-months after surgery, with improved recovery as measured by PROMIS-M and PROMIS-PI measures at 6 weeks, 3 months, 6 months, and 12 months after surgery. We anticipate that the anti-inflammatory effect of lidocaine will reflect a smaller postoperative inflammatory response as measured by IL-10, IL-4, and IL-12.

G Statistical Plan

G1 Sample Size Determination and Power

The target sample size of 50 patients, 25 per group, is based upon a two-tail test at the 0.05 level of significance, with 80% power to detect an effect size of $d=0.8$. Prior data from our institution has shown an average postoperative morphine-equivalent consumption of 149 mg with a standard deviation of 37 mg. The proposed effect size is equivalent to approximately a 20% reduction in postoperative morphine-equivalent opioid consumption. The primary outcome measure is the inpatient measure of postoperative opioid consumption. As such, loss-to-followup is not possible, though 25 per group accounts for 10% loss due to treatment noncompliance which is unlikely.

G2 Analysis Plan

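### Section G1 says 25 per group already allows for 10% loss, but 25 is the number needed with nobody lost

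*Combined protocol and SAP*

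**What the plan says.** Section G1 gives the basis of the sample size: "The target sample size of 50 patients, 25 per group, is based upon a two-tail test at the 0.05 level of significance", with 80% power for a standardised difference of d = 0.8. The planning figures are an "average postoperative morphine-equivalent consumption of 149 mg with a standard deviation of 37 mg", and G1 equates d = 0.8 with a reduction of about 20%. It rules out loss to follow-up because the primary outcome is measured in hospital, but then says of the same number: "though 25 per group accounts for 10% loss due to treatment noncompliance which is unlikely".

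Section E2 repeats the target: "We will enroll 50 patients, 25 per group, over two years". No smaller number before inflation, and no larger enrolment number after it, appears anywhere.

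Sections F3 and I1 both address patients whose study drug is stopped for an intraoperative complication: "The patient will be analyzed in an intent-to-treat analysis, though they will be excluded from as-treated analyses".

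**The concern.** If 25 per group is both what the power calculation requires and a number already enlarged for 10% loss, the calculation must have required about 25 × 0.9 = 22.5 per group. A standardised difference of 0.8 at 80% power and two-sided 0.05 looks too demanding for that.

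G1 is the only sample-size justification for the primary outcome. As written, it tells an ethics committee or a later reader that the trial keeps 80% power under 10% noncompliance. If noncompliance occurred and the result were null, they would think the trial more sensitive than it was.

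**Working it through.** **Inputs, all from G1:** two-sided alpha 0.05, power 80%, d = 0.8, mean 149 mg, SD 37 mg, 25 per group, 10% loss. Allocation is 1:1 (section 2.c). As a check on the effect, 0.8 × 37 = 29.6 mg and 29.6/149 = 19.9%, which agrees with the stated 20%.

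**Reproducing the 25, with nobody lost**

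- Normal approximation: n per group = 2 × ((1.960 + 0.842)/0.8)² = 24.53, so 25.
- Two-sample t-test (noncentral t): 25.52, so 26.
- Taking exactly 20% (29.8/37 = 0.805) gives 24.20 and 25.20, so still 25 and 26.

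The 25 is therefore the no-loss size by the normal approximation, and one short of it by the t-test. A one-sided 0.05 test would need only 20 or 21 per group and would leave room for 10% loss, but G1 specifies a two-tailed test.

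**Power at the planned size and under 10% noncompliance**

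G1 does not say how non-compliers enter the analysis, so both readings are shown. Excluding 10% of 50 leaves 45, or 22 and 23 per group. Under intent-to-treat all 50 remain and the mean difference is diluted: d = 0.8 × (1 − 0.10) = 0.72 if non-compliers keep no benefit, and 0.8 × (1 − 0.05) = 0.76 if they keep half. The retained benefit is an assumption. So is taking d = 0.8 as the effect under full compliance.

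| Scenario | n per group | d | Power, t-test | Power, normal |
|---|---|---|---|---|
| All analysed, full compliance | 25/25 | 0.80 | 79.2% | 80.7% |
| 10% excluded | 22/23 | 0.80 | 74.6% | 76.5% |
| Intent-to-treat, half benefit kept | 25/25 | 0.76 | 75.0% | 76.6% |
| Intent-to-treat, no benefit kept | 25/25 | 0.72 | 70.4% | 72.1% |

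The intent-to-treat rows hold the SD at 37 mg. Adding the extra variance from mixing compliers and non-compliers lowers the t-test figures to 74.7% and 69.1%.

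**Effect detectable at 80% power with 22 and 23 per group**

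- t-test: d = 0.855, which is 0.855 × 37 = 31.6 mg, or 21% of 149 mg.
- Normal approximation: d = 0.835, which is 30.9 mg.

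**What a real 10% allowance would take**

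- For exclusion: 25/0.9 = 27.8, so 28 per group (normal), or 26/0.9 = 28.9, so 29 (t-test).
- For intent-to-treat with no retained benefit (d = 0.72): 30.28, so 31 (normal), or 31.27, so 32 (t-test).

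**The case against.** The strongest reply is that this is one clause about an event G1 calls unlikely, and that the headline 80% is sound. A small error in the planning SD matters as much: with 39 mg instead of 37 mg and the same 29.6 mg difference, t-test power with all 50 analysed is 74.8%. That is fair as to size, and it is why I do not ask for a larger trial. It does not make the clause true.

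A second reply is that the intent-to-treat figures rest on assumptions the plan does not make. If d = 0.8 was meant as the overall effect after noncompliance, diluting it again counts the loss twice. This stands as a caution, and those figures are illustrative. The exclusion result needs only G1's own inputs. And if 0.8 already included noncompliance, the margin would lie in the choice of effect, not in 25 per group, where G1 puts it.

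Third, F3 and I1 speak of drug stopped for complications, not of noncompliance in general. Elsewhere F3 says some patients with intraoperative complications will be excluded from the study, and both sections describe patients with later complications as analysed per protocol. So the primary analysis set is not settled. That also stands; it is the reason both readings are shown, and exclusion from the study would only add to real loss.

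Fourth, G1 names no test, and G2 refers to regression models. Adjustment for a baseline variable might recover some power, but G1 claims no such gain. Nor does the pattern of loss rescue the clause: if the 10% fell in one arm only (25 against 22 or 23), power would be 76–77% by t-test and 78–79% by normal approximation, still under 80%.

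**Conclusion.** The concern holds. On G1's own inputs, 25 per group is the size for full compliance and complete analysis, and it contains no allowance for 10% loss. The 80% claim is essentially right if nobody is lost (79.2% by t-test, 80.7% by normal approximation). Under the 10% scenario G1 names, power falls about 3 to 5 points below 80% if those patients are excluded evenly across arms. Under intent-to-treat it falls about 3 to 10 points below, depending on the benefit they are assumed to retain. The exclusion figures depend on nothing outside G1 except the choice between t-test and normal approximation. The intent-to-treat figures depend also on the retained benefit and on reading d = 0.8 as the full-compliance effect. The error is definite but modest: it concerns what G1 claims for the design and does not undermine the primary comparison.

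**What to change.** Keep 50 patients and delete the claim that 25 per group covers a 10% loss. Replace it with a statement along these lines:

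> With a two-sample t-test at two-sided 0.05, 25 per group gives about 79% power for d = 0.8 (29.6 mg, about 20%) when all patients are analysed (81% by normal approximation). If 10% are excluded, as in an as-treated analysis, power is about 75% (76.5% by normal approximation). If 10% are non-compliant but remain in the intent-to-treat analysis, power depends on the benefit they are assumed to retain: about 70% with none (d = 0.72) and about 75% with half (d = 0.76).

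If the sponsor intends a different primary test, the same sentences should be written with that test's figures. If the sponsor would rather have a true 10% margin, the price is 28 or 29 per group for exclusion, or 31 or 32 under intent-to-treat with no retained benefit. Since G1 regards the loss as unlikely, restating the power is the proportionate choice.

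The cost is a few sentences in G1 and a slightly less favourable stated power. Enrolment, conduct and analysis do not change.
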